7.3 Clinical Activity Evaluable Population

In order to be considered eligible for the clinical activity evaluable population, the patient must have at least one on-study disease assessment or discontinue from treatment for PD. Patients who discontinue treatment prior to the first on-study disease assessment for an AE, toxicity, or withdraw consent are considered non-evaluable for disease assessment and will not be part of the clinical activity evaluable population.

This population will be used to present tumor responses as well as to make decision on the Predictive Probability design.

7.4 Safety Population

The safety population is defined as all patients who received at least 1 dose of either mocetinostat or durvalumab. The safety population will be used for all safety analyses.

Sponsor: Mirati Therapeutics, Inc.

Protocol no: 0103-020

7.5 DLT Evaluatable Population

For a patient to be considered evaluable for dose-escalation decisions, or “DLT-evaluable,” the patient must have either been on study for 1 full cycle and have received treatment with durvalumab and at least 9 of 12 scheduled mocetinostat doses (75%) in Cycle 1 or have experienced a DLT in Cycle 1.

Note that the DLT evaluation period does not include the 7 day run in of mocetinostat.

7.6 Molecular Marker Evaluatable Population

The molecular marker evaluable population will consist of all patients who receive at least one dose of mocetinostat or durvalumab for whom PD-L1 expression results are available.

7.7 Pharmacokinetic Evaluatable Population

The pharmacokinetic evaluable population will consist of all patients who had sufficient concentration-time data to permit calculation of PK parameters for mocetinostat or durvalumab. For patients who were noncompliant with respect to administration of mocetinostat, or for patients with incomplete data, a decision as to their inclusion in the analysis will be made on a case-by-case basis.

The PK analyses will be described in a PK analysis plan separate from this document.

7.8 Pharmacodynamic Evaluatable Population

The pharmacodynamic evaluable population will consist of all patients who receive at least one dose of either mocetinostat or durvalumab for whom pharmacodynamic results are available.

7.9 Anti-Drug Antibody Evaluatable Population

The ADA evaluable population will consist of all patients who receive at least one dose of either mocetinostat or durvalumab for whom ADA results are available.

8.0 Endpoint Definitions

8.1 Efficacy Variables

Disease assessments involving radiographic evaluations may be performed over the course of a few days. The date of response or progression (CR, PR, SD, PD or NE) will be recorded as the date of the last radiographic evaluation included in the series for that time point assessment. For central review (if this is done), the date of response or progression will be determined using the Date of Assessment associated with the applicable Time Point Assessment provided by the central review vendor; for the investigator assessment, the date will be determined using the latest Date of Assessment recorded among the radiologic modalities included for the applicable Time Point Assessment.

8.1.1 Objective Response Rate ORR)

Objective disease response will be categorized in accordance with RECIST v1.1. ORR is defined as the proportion of patients documented to have a confirmed CR or PR. If central review of disease response is undertaken, ORR as reported by the central radiology review laboratory will be used to calculate ORR and the exact binomial 95% CIs. ORR as reported by the investigator will be used in study expansion and decision making (PPD design).

Sponsor: Mirati Therapeutics, Inc.

Protocol no: 0103-020

8.1.2 Best Overall Response

Best Overall Response is defined as the best response among all overall responses (in the order complete response [CR], partial response [PR], stable disease [SD], progressive disease [PD] and not evaluable [NE]) recorded from the start of study treatment until disease progression/ recurrence or end of the treatment, whichever comes first. Per RECIST version 1.1, the status of best overall response of PR or CR must be confirmed by repeat tumor assessment within no less than 4 weeks. If the status of CR or PR cannot be confirmed by repeat tumor assessment, the best overall response of unconfirmed CR and PR will be recorded as SD and NE. The status of best overall response of SD requires an on-study assessment after at least 35 days on treatment.

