## 7.2 Efficacy

All patients enrolled in the study are to be evaluated for disease activity as outlined in the Schedule of Assessments (Table 1). Screening/baseline tumor assessments should include CT or MRI of the chest, abdomen, and pelvis, whole body bone scan, MRI of the brain and evaluation of any superficial lesions. On-study assessments will include all known and suspected sites of disease and will be performed at 8 week intervals until approximately 1-year and then every 12 weeks. The allowable windows for assessments are 4 weeks prior to first study treatment for screening/baseline assessments and  $\pm 10$  days for on-study disease assessments.

CT scans should be performed with contrast agents unless contraindicated for medical reasons. If intravenous contrast is medically contraindicated, the imaging modality to be used (either CT without contrast or MRI) should be the modality which best evaluates the disease, and the choice should be determined by the investigator in conjunction with the local radiologist. Depending on the adequacy for evaluation of disease, a combination of CT without contrast and MRI should most often be used. CT without contrast is preferred for evaluation of lesions in lung parenchyma. MRI is not adequate for evaluation of lung parenchyma but should also be performed to evaluate all other aspects of the chest. MRI of the abdomen and pelvis should substitute for CT with contrast unless the method does not adequately depict the individual's disease, in which case CT without contrast is preferred. For those sites that routinely use PET scans for assessment of bone lesions in lieu of skeletal scintigraphy, PET scans may be used on-study, with the same modality planned throughout the study for any given patient.

For patients having effusions or ascites, cytological proof of malignancy should be obtained prior to selection of the effusion as a non-target lesion. Effusions that have not been evaluated using cytology or were found to be non-malignant should not be considered to be cancer lesions.

Disease response will be assessed in accordance with RECIST 1.1 (Eisenhauer-2009). Appendix 5 provides guidance in using the response criteria and include a modification to RECIST 1.1 to address potential temporary treatment effects such as tumor lesion cavitation or flare response. Assessments will be performed until objective disease progression is documented by the investigator, or subsequent anti-cancer therapy is begun.

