Patients experiencing tumor response (Partial Response [PR] or Complete Response [CR]) should undergo confirmatory assessment at least 4 weeks after initial documentation of response. It is acceptable to perform confirmatory assessments at the next appointed evaluation per protocol. Bone scan is required as an element of the confirmation of PR or CR if bone lesions were identified at the baseline assessment.

The investigator's assessment of disease response and progression will be the basis for patient management and study expansion decision making. Potential exists for individual tumor lesions to cavitate or become otherwise difficult to evaluate for a period of time as the result of beneficial study treatment impact. For example, tumor necrosis and cavitation may result in minor increase in overall individual lesion size or unclear tumor margins prior to recovery to a smaller lesion, development of scar tissue, or complete resolution. For this reason, investigators may delay reaching the conclusion of disease progression until subsequent on-study disease assessments are performed.

Central radiology review to assess RECIST outcome may be undertaken after Stage 1 of the study. Materials to be forwarded for independent review will be all imaging studies performed at screening and on study, preferably in digital format, using an electronic transfer through a portal to the review vendor or transfer on compact disc or optical disc. All digital media must be in DICOM format. Films may be forwarded for review if necessary; all films should be originals (second original films acceptable) rather than copies of films.

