***Best Objective Response***

Target Lesions	Non-Target Lesions	New Lesion	Point in Time Response	Best Response
CR	CR	No	CR	CR and PR require confirmation at least 4 weeks after first observation
CR	Non-CR/Non-PD	No	PR	
PR	Non-PD	No	PR	
SD	Non-PD	No	SD	SD requires an on-study assessment after at least 6 weeks on treatment. Unconfirmed PR or CR are reported as SD.
PD	Any	Yes or No	PD	
Any	PD	Yes or No	PD	
Any	Any	Yes	PD	

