8.1.4 Duration of Response (DR)

DR is defined as the time in days from date of the first documentation of objective response (CR or PR) to the first documentation of objective progression of disease (PD) or to death due to any cause in the absence of documented PD (i.e., min [PD date, death date] – date of the first observation of response +1). Duration of response will only be calculated for the subgroup of patient achieving a Best Overall Response of CR or PR and will be presented for responses assessed by both central review and investigator's assessment.

Censoring rules will be applied to DR:

- Event time will be censored on the date of the last evaluable assessment documenting response for:
 - Patients on-study and progression-free at the time of an analysis;
 - Patients who have PD or death on study after ≥ 2 consecutive missed tumor assessments (i.e., >12 weeks + 14 days after the last on-study disease assessment);
 - Patients given alternative cancer treatment prior to PD or death on-study.
- Patients who die on-study after ≥ 2 consecutive missed tumor assessments (i.e., >12 weeks + 14 days after the last on-study disease assessment) will have their event time censored on the date of the last evaluable assessment documenting response.

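### SAP 8.1.2 ends best overall response at end of treatment while Protocol 7.2 keeps scanning, so BOR and duration of response can omit confirmed responders whom the ORR definition counts

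*SAP*

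**What the plan says.** **BOR window.** SAP 8.1.2 ranks the overall responses "recorded from the start of study treatment until disease progression/ recurrence or end of the treatment, whichever comes first". A CR or PR "must be confirmed by repeat tumor assessment within no less than 4 weeks". If it is not confirmed, "the best overall response of unconfirmed CR and PR will be recorded as SD and NE", so either way it is not a response.

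**Scanning period.** Protocol 7.2 says: "Assessments will be performed until objective disease progression is documented by the investigator, or subsequent anti-cancer therapy is begun". End of treatment is not a stopping point there. Scans "will be performed at 8 week intervals until approximately 1-year and then every 12 weeks". On confirmation, Protocol 7.2 adds: "It is acceptable to perform confirmatory assessments at the next appointed evaluation per protocol".

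**Protocol best-response rule.** The Best Objective Response table in Protocol Appendix 5 says "CR and PR require confirmation at least 4 weeks after first observation" and sets no end-of-treatment limit.

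**Duration of response.** SAP 8.1.4: "Duration of response will only be calculated for the subgroup of patient achieving a Best Overall Response of CR or PR".

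**ORR.** Protocol 9.4.1 and SAP 8.1.1 both define it as confirmed CR or PR. Neither states a window or refers to BOR.

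**The concern.** Confirmation takes at least 4 weeks and may wait for the next scheduled scan, which is 8 weeks later in the first year. Take a patient with a first PR at about Week 8 who stops for toxicity and is confirmed at Week 12 to 16, with no progression and no new therapy in between. Protocol 7.2 calls for the confirming scan, but that scan falls after the date on which SAP 8.1.2 closes the window. A patient whose first response appears only after stopping is in a worse position, because no part of that response lies inside the window.

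The direct stake is consistency. Under its own definition ORR could count such a patient, while the BOR table shows a non-responder and the duration-of-response analysis leaves the patient out. The indirect stake is the primary endpoint: if ORR is derived from BOR in programming, it loses genuine responders. The stated power exceeds the required 0.90 by less than 0.005, so there is little room for such a loss.

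The closing date is also not well defined. SAP Appendix 4 describes separate End of Treatment pages for mocetinostat and durvalumab, and SAP 8.1.2 does not say whether stopping one drug or both closes the window.

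**Working it through.** **1. Where each response variable stops**

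| Item | Stops at | Source |
|---|---|---|
| Scanning | Progression or new anti-cancer therapy | Protocol 7.2 |
| ORR | No window stated | Protocol 9.4.1, SAP 8.1.1 |
| PFS | Censored at new therapy, not at end of treatment | Protocol 9.4.4, SAP 8.1.6 |
| Duration of response | Censored at new therapy, but entry requires a BOR of CR or PR | SAP 8.1.4 |
| BOR | Progression/recurrence or end of treatment | SAP 8.1.2 |

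BOR is the only item cut at end of treatment.

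**2. Which patients are affected**

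- First response after end of treatment: outside BOR on any reading.
- First response on treatment, confirmed after end of treatment: outside BOR if the confirming scan must itself lie in the window, inside if it need not. The text does not settle this.
- Stopped for an adverse event before any on-study scan: already outside the clinical activity evaluable population (SAP 7.3), so not part of this point.

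**3. The plan's own design figures**

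Inputs from SAP 6.3.3 and 6.3.4:

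- Cohorts 1, 3 and 4: n1 = 9, continue if at least 1 response; n = 17, success if at least 3; p0 = 0.05, p1 = 0.30.
- Cohort 2: n1 = 17, continue if at least 5; n = 44, success if at least 18; p0 = 0.27, p1 = 0.50.

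Formula: P(success) = sum over x from r1 to n1 of P[Bin(n1, p) = x] × P[Bin(n − n1, p) ≥ r − x].

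For Cohorts 1, 3 and 4 at p = 0.30, failure can occur in three ways:

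- no response in 9: 0.7^9 = 0.0404
- one response in 9, then at most one in 8: 0.1556 × 0.2553 = 0.0397
- two responses in 9, then none in 8: 0.2668 × 0.0576 = 0.0154

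The total is 0.0955, so power is 0.9045. Type 1 error is 0.0466 and early termination under the null is 0.95^9 = 0.6302. For Cohort 2 the same sum gives power 0.9018, type 1 error 0.0303 and early termination 0.4977. All match the stated values.

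**4. Sensitivity, only if ORR follows BOR**

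Let q be the share of true responders lost. The documents do not give q, so it is an assumption. The effective response rate is p1 × (1 − q). At q = 5% in Cohorts 1, 3 and 4, p = 0.30 × 0.95 = 0.285. The three failure terms become 0.0488 + 0.0501 + 0.0191 = 0.1180, so power is 0.882.

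| q | Cohorts 1, 3, 4: p | Power | Cohort 2: p | Power |
|---|---|---|---|---|
| 0 | 0.300 | 0.9045 | 0.500 | 0.9018 |
| 1% | 0.297 | 0.900 | 0.495 | 0.890 |
| 3% | 0.291 | 0.891 | 0.485 | 0.864 |
| 5% | 0.285 | 0.882 | 0.475 | 0.834 |
| 10% | 0.270 | 0.855 | 0.450 | 0.741 |

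At 1%, Cohorts 1, 3 and 4 still just meet the constraint (0.9003).

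SAP 6.2 lets unconfirmed responses serve as the initial basis for expansion. If the Stage 1 decision uses all responses and only the final count is cut, power at q = 5% and 10% is 0.885 and 0.862 in Cohorts 1, 3 and 4, and 0.840 and 0.751 in Cohort 2. The change is small.

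**The case against.** A reader might infer that the primary endpoint is biased and the trial underpowered. The documents do not support that. ORR has no end-of-treatment limit in either document, neither definition cites BOR, and SAP 12.5.1 lists ORR, CBR and BOR as separate items. ORR falls only if it is programmed from BOR. This objection stands, and the power figures are conditional on it.

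A reader might also infer that every response confirmed after stopping is lost. The confirmation sentence in SAP 8.1.2 carries no window of its own, so a PR first seen on treatment could fairly be confirmed later. That stands as a possible reading. It does not rescue a response first seen after stopping.

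The loss share has no direct support. The documents give no discontinuation rate for the combination. The 6.5% in Protocol 1.3.3 (29 of 444) is for durvalumab alone, for any adverse event at any time. A loss on the stricter reading needs a responder who stops between two particular scans, neither progresses nor starts new therapy, and is then confirmed. A share of 10% cannot be excluded, but nothing in the documents points to it.

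Finally, Protocol Table 1 does not clearly place imaging in the post-treatment column, and its long-term follow-up footnote lists survival, later therapies, PK and ADA but not scans. Section 7.2 is the explicit text and supports continued scanning, but how consistently sites will scan after treatment is less certain.

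**Conclusion.** The point holds as an inconsistency between the SAP and the protocol, and within the SAP. Following SAP 8.1.2 as written removes from BOR, and hence from the duration-of-response subgroup, any response first seen after treatment stops. On the stricter reading it also removes responses confirmed after treatment stops. ORR as defined keeps both groups, so the SAP supports two different responder counts.

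Bias in the primary ORR is possible but not shown, since the SAP does not say whether ORR is derived from BOR. If it is, the effect depends on an unknown loss share. Over an assumed 1% to 10%, power runs from 0.900 to 0.855 in Cohorts 1, 3 and 4 and from 0.890 to 0.741 in Cohort 2. Cohort 2 falls below the 0.90 constraint across that whole range; the other cohorts do so at 3% and above. Because the correction is short, it should be made even though the size is unknown.

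**What to change.** In SAP 8.1.2:

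- Replace the end of the BOR window with: *until documented objective progression or start of subsequent anti-cancer therapy, whichever comes first*. This matches Protocol 7.2 and removes the question of which drug's end of treatment closes the window.
- State that the confirming scan may fall after end of treatment, provided it lies within that window.
- State that ORR and the duration-of-response subgroup use the same confirmed responders as BOR.

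Leave the event and censoring rules for duration of response as they are. That endpoint counts deaths, which can follow the last scan, so the BOR window should not be applied to it. Leave the CBR duration rule unchanged as well.

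The cost is a few sentences, which can go into the final SAP version planned before database lock (SAP 4.0). No assessments beyond Protocol 7.2 are needed. The small downside is that a few responses seen after treatment has stopped will count.

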8.1.3 Clinical Benefit Rate (CBR)

CBR response will be categorized in accordance with RECIST v1.1. CBR is defined as the proportion of patients documented to have a confirmed CR or PR or SD documented during at least 2 on-study assessments and including at least 14 weeks on study (e.g., allowance for 2-week window around Week 17 assessment).

8.1.4 Duration of Response (DR)

DR is defined as the time in days from date of the first documentation of objective response (CR or PR) to the first documentation of objective progression of disease (PD) or to death due to any cause in the absence of documented PD (i.e., min [PD date, death date] – date of the first observation of response +1). Duration of response will only be calculated for the subgroup of patient achieving a Best Overall Response of CR or PR and will be presented for responses assessed by both central review and investigator's assessment.

Censoring rules will be applied to DR:

- Event time will be censored on the date of the last evaluable assessment documenting response for:
 - Patients on-study and progression-free at the time of an analysis;
 - Patients who have PD or death on study after ≥ 2 consecutive missed tumor assessments (i.e., >12 weeks + 14 days after the last on-study disease assessment);
 - Patients given alternative cancer treatment prior to PD or death on-study.
- Patients who die on-study after ≥ 2 consecutive missed tumor assessments (i.e., >12 weeks + 14 days after the last on-study disease assessment) will have their event time censored on the date of the last evaluable assessment documenting response.

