#### **9.4.3 Duration of Response**

Duration of Response (DR) is defined as the time from date of the first documentation of objective tumor response (CR or PR) to the first documentation of Objective Progression of Disease (PD) or to death due to any cause in the absence of documented PD. Censoring for the DR endpoint will be assigned on the date of the last tumor assessment if no assessment of tumor progression is identified and the patient does not die while on study. DR will only be calculated for the subgroup of patients with an objective response. The Kaplan-Meier method will be used to obtain the estimate of median DR.

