#### **9.4.4 Progression Free Survival**

Progression-free survival (PFS) is defined as the time from date of first study treatment to first PD or death due to any cause in the absence of documented PD. Censoring for the PFS endpoint will be assigned on the date of the last tumor assessment if no assessment of tumor progression is identified and the patient does not die while on study. For patients in whom two or more sequential assessments are missed, followed by the finding of tumor progression, the PFS endpoint will be censored on the date of the last tumor assessment before the gap. Patients lacking an evaluation of disease after first study treatment will have their PFS time censored on the date of first dose with duration of 1 day. Patients who start a new anti-cancer therapy prior to documented PD will have the endpoint censored at the date of the last tumor assessment prior to the start of the new therapy. The Kaplan-Meier method will be used to obtain the estimate of median progression-free survival time.

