### **Target Disease**

- Complete Response (CR): Complete disappearance of all target lesions with the exception of nodal disease. All target nodes must decrease to normal size (short axis < 10 mm). All target lesions must be assessed.
- Partial Response (PR): Greater than or equal to 30% decrease under baseline of the sum of diameters of all target measurable lesions. The short diameter is used in the sum for target nodes, while the longest diameter is used in the sum for all other target lesions. All target lesions must be assessed.
- Stable Disease (SD): Does not qualify for CR, PR or Progression. All target lesions must be assessed. Stable can follow PR only in the rare case that the sum increases by less than 20% from the nadir, but enough that a previously documented 30% decrease no longer holds.
- Progressive Disease (PD): 20% increase in the sum of diameters of target measurable lesions above the smallest sum observed (over baseline if no decrease in the sum is observed during therapy) with a minimum absolute increase of 5 mm.
- Indeterminate: Progression has not been documented, and
  - one or more target lesions have not been assessed,
  - or assessment methods used were inconsistent with those used at baseline and impaired assessment,
  - or one or more target lesions cannot be measured accurately (eg, poorly visible unless due to being too small to measure),
  - or one or more target lesions were excised or irradiated and have not reappeared or increased.

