8.1.6 Progression-Free Survival (PFS)

PFS is defined as the time from the first dose of study drug to the date of PD or death due to any cause, whichever occurs first. PFS (in months) will be calculated as (first event date – first dose date +1)/30.4.

Censoring rules will be applied to PFS:

Sponsor: Mirati Therapeutics, Inc.

Protocol no: 0103-020

- Patients lacking evaluation of disease after first study treatment will have their PFS time censored on the date of first dose with duration of 1 day unless they die within 2 tumor assessments of baseline, then they will be treated as an event with date of death as the event date.
- Patients with baseline or post-baseline assessments inadequate to apply RECIST criteria will have their event time censored on the date of the first dose of study drug.
- Event time will be censored on the date of the last evaluable assessment documenting absence of PD for:
 - Patients on-study and progression-free at the time of an analysis;
 - Patients who have PD or death on study after ≥ 2 consecutive missed tumor assessments (i.e., >12 weeks + 14 days after the last on-study disease assessment);
 - Patients given alternative cancer treatment prior to PD or death on-study.
- Patients who die on-study after ≥ 2 consecutive missed tumor assessments (i.e., >12 weeks + 14 days after the last on-study disease assessment) will have their event time censored on the date of the last evaluable assessment documenting absence of PD.

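### SAP 8.1.4 censors duration of response at the last scan that still shows response, so a censored responder who has drifted to stable disease loses progression-free follow-up that Protocol 9.4.3 and the SAP's own PFS rule would keep

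*SAP*

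**What the plan says.** SAP 8.1.4 measures DR from the date of first response, and the end point of the interval is given as "to the first documentation of objective progression of disease (PD) or to death due to any cause in the absence of documented PD". Falling back from PR to SD is therefore not an event.

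The censoring rule in the same section is "Event time will be censored on the date of the last evaluable assessment documenting response for" three groups. The first is "Patients on-study and progression-free at the time of an analysis". The second is patients whose PD or death comes after at least two consecutive missed assessments, and the third is patients given other cancer treatment before PD or death. A second bullet repeats the rule for deaths after missed assessments, with the same censoring date.

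SAP 8.1.6 (PFS) lists the same three groups but words the date differently: "Event time will be censored on the date of the last evaluable assessment documenting absence of PD for" those groups.

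Protocol 9.4.3 gives this rule for DR: "Censoring for the DR endpoint will be assigned on the date of the last tumor assessment if no assessment of tumor progression is identified". It is limited to patients who have not died on study, and it does not require that scan still to show response. Protocol 9.4.4 uses the same formula for PFS.

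Protocol Appendix 5 allows the situation in which the wordings diverge: "Stable can follow PR only in the rare case that the sum increases by less than 20% from the nadir", yet by enough that the 30% decrease is lost.

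**The concern.** The event and the censoring date do not fit together. A responder whose tumor sum creeps back above the PR threshold without reaching PD is still event-free. If PD or death is later seen on schedule, DR runs to that date and the SD period counts as time in response. If the patient is instead censored, the same SD scans are dropped and DR stops at the last PR scan. Whether observed follow-up counts thus depends on what happens afterwards.

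The drop is triggered by regrowth, which plausibly signals approaching progression, so the censoring is informative. Event-free patients leave the risk set early while those who progress stay in until their event, so the Kaplan-Meier curve for DR tends to be too low. The same patient's PFS is censored at a later scan than DR, and DR departs from Protocol 9.4.3 without a stated reason.

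**Working it through.** The documents give no DR sample size, event count or median, so there is no planned figure to reproduce. The check has three parts.

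**1. When can SD follow PR?** Inputs, from Protocol Appendix 5: PR is "Greater than or equal to 30% decrease under baseline of the sum of diameters of all target measurable lesions"; PD is a 20% rise from the smallest sum, with at least 5 mm absolute increase.
- Loss of PR needs a sum above 70% of baseline.
- No PD by the percentage rule needs a sum below 1.2 × nadir.
- Both hold only if nadir > 0.70 / 1.2 = 58.3% of baseline. Because the patient reached PR, nadir is at most 70%.
- Best shrinkage therefore lies between 30% and 41.7%. The window widens only where the 5 mm minimum governs, which is for baseline sums below 5 / (0.70 − 0.5833) ≈ 43 mm.

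The case is possible, but confined to fairly shallow responses.

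**2. One patient.** This responder is hypothetical, on the 8-week schedule, with days counted from Cycle 1 Day 1: PR at Weeks 9 and 17 (Days 57 and 113), SD at Weeks 25 and 33 (Days 169 and 225), no PD at cut-off. The formula in SAP 8.1.4 is end date − first response date + 1.
- SAP 8.1.4, literal: 113 − 57 + 1 = 57 days.
- Protocol 9.4.3: 225 − 57 + 1 = 169 days.
- Difference: 169 − 57 = 112 days, or two scan intervals. PFS for this patient is censored at the Day 225 scan.

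**3. Size across a responder group.** The documents do not give the inputs, so these are assumptions: exponential DR with a 12-month median, follow-up uniform over 3 to 18 months, scans every 56 days, PR lost at half the time to PD in those who pass through SD, and 20,000 simulated responders per row. Only ongoing responders are censored; new therapy and missed scans are not modelled.

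| Responders passing through SD | Censored earlier under SAP | 12-month DR, protocol rule | 12-month DR, SAP rule | Difference (points) |
|---|---|---|---|---|
| 0% | 0% | 0.526 | 0.526 | 0 |
| 10% | 2% | 0.529 | 0.524 | 0.5 |
| 20% | 4% | 0.523 | 0.515 | 0.8 |
| 30% | 7% | 0.520 | 0.505 | 1.5 |
| 50% | 11% | 0.530 | 0.505 | 2.5 |

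Comparisons are valid within a row; each row is a fresh sample. The median was 12.9 months under both rules in every row. It is resolved only to the scan grid (56 / 30.4 = 1.84 months), so a smaller shift would not show.

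**The case against.** Four points can fairly be made for the plan.

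- **The SAP may do this.** Protocol 9 lets the SAP modify the protocol's plans, requiring an amendment as well only for major changes to the primary endpoint. Protocol 9.2 leaves specific censoring rules to the SAP, and DR is a secondary endpoint summarized descriptively. This stands: a reader might infer a breach of the protocol, and the documents do not support that. What remains is an unexplained inconsistency.
- **The wording may be loose.** SAP 8.1 and 8.1.2 use the word response for any RECIST category, including SD, so the bullet might mean any scan with a recorded status. That is possible. But 8.1.6 names the same groups and uses a different phrase, so a programmer would most naturally take 8.1.4 literally. If the wording is only loose, correcting it changes no intent.
- **Few patients are touched.** A reader might infer that SD scans are discarded in all responders. They are not: a responder with SD and then timely PD or death keeps the full DR. Appendix 5 also calls SD after PR rare. Both points stand and limit the size.
- **The damage to DR summaries is easily overstated.** A reader might infer a distorted Kaplan-Meier median, but the simulation shows no shift at scan resolution. Nor is one affected patient 20% of a cohort's DR data. At the 30% target about 5 of 17 patients respond (0.30 × 17 = 5.1), so one is 20% of responders, and that patient still contributes follow-up to the last PR scan. The share falls to 1 in 22 (4.5%) in Cohort 2 at its 50% target (0.50 × 44) and to 1 in 30 (3.3%) in a cohort expanded to 100 at 30%.

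**Conclusion.** The inconsistency is real and should be corrected, but it is minor. On its literal wording, SAP 8.1.4 removes progression-free follow-up from responders who drift to SD and are then censored, in conflict with SAP 8.1.6 for the same groups and with Protocol 9.4.3 for ongoing progression-free responders. The direction is conservative: DR tends to be understated. A loss of about 0.5 to 2.5 percentage points on 12-month DR rests on the simulation's assumed median, follow-up and timing of PR loss, and on 10 to 50% of responders passing through SD. As the protocol calls this rare, the lower end is the more plausible. For one patient the loss can be large, as the 112-day example shows, and this is most visible in a cohort with about five responders. The ORR analysis and its type 1 error and power do not use this rule.

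**What to change.** In both censoring bullets of SAP 8.1.4, replace *documenting response* with *documenting absence of PD*, the phrase already used in 8.1.6. This aligns DR with the SAP's PFS rule, and with Protocol 9.4.3 for responders who are progression-free at the analysis.

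It does not make the two documents identical. Protocol 9.4.3 has no DR censoring for missed assessments or new anticancer therapy; the protocol gives those rules only for PFS, in 9.4.4. The SAP should say that these are its own additions for DR. If censoring at the last response scan is intended, the SAP should instead state and justify it as a departure from 9.4.3.

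The cost is a few words and one explanatory sentence, with no new data or patients. The change can go into SAP2, which SAP 4.0 schedules before database lock; the DR derivation needs changing only if the literal rule has already been programmed.
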